#### **10.1.7 Pregnancy reporting**

For the requirements on pregnancy tests see [Section 8.4.8](#), and for the requirements on contraception see [Appendix 1](#).

If a female trial participant becomes pregnant, the study treatment should be stopped, and the trial participant must be asked to read and sign pregnancy consent form to allow the Study Doctor ask about her pregnancy. To ensure participant safety, each pregnancy occurring after signing the informed consent must be reported to Sponsor using a pregnancy reporting form within 24 hours of learning of its occurrence until the end of follow-up period. The pregnancy should be followed up to determine outcome, including spontaneous or voluntary termination, details of the birth, and the presence or absence of any birth defects, congenital abnormalities, or maternal and/or newborn complications. The newborn should be followed-up until one year after he/she was due to be born. Pregnancy follow-up should be recorded on the same form and should include an assessment of the possible relationship to the Lutathera treatment and any pregnancy outcome. Any SAE experienced during pregnancy must be reported.

Pregnancy outcomes should also be collected for the female partners of any males who received Lutathera in this study until the end of follow-up period. Consent to report information regarding these pregnancy outcomes should be obtained from the female partner.

#### **10.1.8 Reporting of study treatment errors including misuse/abuse**

Neither overdose nor drug abuse/misuse are expected to be a concern with Lutathera, because it is administered by a trained clinician with appropriate prior training and provided as a single-dose, ready-to-use product containing a predefined amount of radioactivity.

Any AE/SAE/AESI in connection with radiation overdose must be reported as per the general reporting rules.

### 10.1.9 Reporting rules: summary

The below table summarize all reporting rules and timeframes for safety data reporting (SAE form) to sponsor global safety database described in the above sections:

**Table 10-2 Reporting rules and timeframe**

| Event           | During Screening                                     | During Treatment period  | During Follow-up period   | Reporting timeframe          |
|-----------------|--|--|---|------------------------------|
| Non-serious AEs | Not reported   | Not reported   | Not reported  | Not applicable               |
| SAEs            | Only SAEs potentially related to any study procedure | All SAEs, regardless of causality, until 8 weeks + 30 days after last dose | SAEs to be reported only if the investigator suspects a causal relationship to study treatment  | Within 24 hours of awareness |
| AESI            | Only if SAE, see above                               | All AESI irrespective of causality   | AESI to be reported only if considered related to the study treatment except for all secondary malignancies which need to be reported as AESI irrespective of causality | Within 24 hours of awareness |
| Pregnancy       | To be reported                                       | To be reported   | To be reported  | within 24 hours of awareness |

## 10.2 Additional Safety Monitoring

### 10.2.1 Data and Safety Monitoring Board

An independent Data and Safety Monitoring Board (DSMB) will be commissioned by the Sponsor to evaluate accumulating safety and dosimetry data in patients enrolled in the study, to ensure the safety of the patients in the study, and to provide recommendations to investigators and to the clinical teams in charge of conducting the study.

The DSMB will comprise one or several experts in the field of oncology, pediatrics and nuclear medicine. All DSMB members will disclose their financial interests to the sponsor. The DSMB will function independently of all other individuals associated with the conduct of this clinical trial, including the site investigators participating in the study. The DSMB will assess at defined intervals the progress of the clinical trial, including safety and dosimetry data for individual patients if applicable, and recommend to the sponsor whether to continue, modify, or terminate a trial. In addition, the DSMB might take decisions for treatment continuation of individual patients.

Specific details regarding composition, responsibilities, data monitoring, and meeting frequency, and documentation of DSMB reports, minutes, and recommendations will be described in a separate charter that is established between the sponsor and the DSMB.

## **11 Data Collection and Database management**

### **11.1 Data collection**

Designated investigator staff will enter the data required by the protocol into the Electronic Case Report Forms (eCRF). The eCRFs have been built using fully validated secure web-enabled software that conforms to 21 CFR Part 11 requirements. Investigator site staff will not be given access to the EDC system until they have been trained. Automatic validation programs check for data discrepancies in the eCRFs, allow modification and/or verification of the entered data by the investigator staff.

The investigator/designee is responsible for assuring that the data (recorded on CRFs) (entered into eCRF) is complete, accurate, and that entry and updates are performed in a timely manner. The Investigator must certify that the data entered are complete and accurate.

After final database lock, the investigator will receive copies of the participant data for archiving at the investigational site.

All data should be recorded, handled, and stored in a way that allows its accurate reporting, interpretation, and verification.

### **11.2 Database management and quality control**

Sponsor personnel (and/or designated CRO) will review the data entered by investigational staff for completeness and accuracy. Electronic data queries stating the nature of the problem and requesting clarification will be created for discrepancies and missing values and sent to the investigational site via the EDC system. Designated investigator site staff are required to respond promptly to queries and to make any necessary changes to the data.

Concomitant treatments and prior medications entered into the database will be coded using the World Health Organization (WHO) Drug Reference List, which employs the Anatomical Therapeutic Chemical classification system. Medical history/current medical conditions and adverse events will be coded using the Medical Dictionary for Regulatory Activities (MedDRA) terminology.

Once all the necessary actions have been completed and the database has been declared to be complete and accurate, it will be locked and made available for data analysis. Any changes to the database after that time can only be made after written agreement by the Sponsor.

### **11.3 Site monitoring**

Before study initiation, at a site initiation visit or at an investigator's meeting, a Sponsor representative will review the protocol and data capture requirements (i.e. eSource DDE or eCRFs) with the investigators and their staff. During the study, Sponsor employs several methods of ensuring protocol and GCP compliance and the quality/integrity of the sites' data. The field monitor will visit the site to check the completeness of participant records, the accuracy of data capture / data entry, the adherence to the protocol and to Good Clinical Practice, the progress of enrollment, and to ensure that study treatment is being stored, dispensed, and accounted for according to specifications. Key study personnel must be available to assist the field monitor during these visits.

Continuous remote monitoring of each site's data may be performed by the Sponsor or a delegated CRO. Additionally, a central analytics organization may analyze data & identify

risks & trends for site operational parameters and provide reports to Sponsor clinical teams to assist with trial oversight.

The investigator must maintain source documents for each participant in the study, consisting of case and visit notes (hospital or clinic medical records) containing demographic and medical information, laboratory data, electrocardiograms, and the results of any other tests or assessments. All information on CRFs must be traceable to these source documents in the participant's file. The investigator must also keep the original informed consent form signed by the participant (a signed copy is given to the participant).

The investigator must give the monitor access to all relevant source documents to confirm their consistency with the data capture and/or data entry. Sponsor monitoring standards require full verification for the presence of informed consent, adherence to the inclusion/exclusion criteria, documentation of SAEs, and of data that will be used for all primary variables. Additional checks of the consistency of the source data with the CRFs are performed according to the study-specific monitoring plan. No information in source documents about the identity of the participants will be disclosed.

## **12 Data analysis and statistical methods**

The data will be analyzed by the Sponsor and/or designated CRO.

All statistical analyses will be descriptive in nature and will include summaries and graphical presentations of data. No statistical hypothesis will be tested.

Missing data will not be replaced in this study.

Interim analyses will be performed to evaluate dosimetry and safety when at least five patients (including at least two GEP-NET patients) have completed at least one cycle. The data from all completed treatment cycles will be presented. Analysis will be presented across both indications, as well as for GEP-NET and PPGL separately.

The primary analysis will be conducted after at least 8 patients (including at least 3 GEP-NET patients) have completed the first cycle (cut-off before the second dose of Lutathera), at which time both dosimetry and safety assessments of the first cycle will be complete for the assessment of the primary objective. Should the dosimetry assessments be done at a further cycle instead of first cycle, the primary analysis will be done after the dosimetry assessments are performed. All data available at the time of primary analysis will be used for the assessment of the primary and secondary objectives, including analysis of the GEP-NETs and PPGLs as a pooled cohort

A final analysis will be performed after all subjects who have received at least one dose of Lutathera have completed the 5 years of follow-up or have withdrawn from the study.

Any data analysis carried out independently by the investigator should be submitted to Sponsor before publication or presentation.

## **12.1 Analysis sets**

The full analysis set (FAS) will include all participants that received at least one dose of Lutathera and will thus be equivalent to the safety analysis set (SAF).

The Dosimetry and PK analysis set will include all participants with at least one available valid (i.e. not flagged for exclusion) dosimetry measurement, who received at least one dose of Lutathera and have no protocol deviations that have an impact on dosimetry data.

## **12.2 Participant demographics and other baseline characteristics**

Demographic and other baseline data including disease characteristics will be listed and summarized descriptively for all participants for the FAS.

Categorical data will be presented as frequencies and percentages. For continuous data, mean, standard deviation, median, minimum, and maximum will be presented.

Relevant medical histories and current medical conditions at baseline will be summarized by system organ class and preferred term for all participants.

## **12.3 Treatments**

The FAS will be used for the analyses below.

The cumulative dose (MBq) will be summarized by means of descriptive statistics. The number of subjects who have dose reductions, permanent discontinuations or interruptions, and the reasons will also be summarized.

Concomitant medications and significant non-drug therapies prior to and after the start of the study treatment will be listed and summarized according to the Anatomical Therapeutic Chemical (ATC) classification system for all participants.

## **12.4 Analysis of the primary endpoints**

The primary aims of the study are to evaluate organ radiation doses as well as safety and tolerability of Lutathera in adolescent patients with SSTR-positive GEP-NETs and PPGL as a pooled cohort.

### **12.4.1 Definition of primary endpoints**

#### **Dosimetry**

The analysis of dosimetry primary endpoint will consist of descriptive summaries and graphical presentations of the derived parameters. The Lutathera dosimetry and absorbed dose in critical organs (e.g. kidney, bone marrow) will be determined from Time activity Curves (TACs). Regions of interest (ROI) will be drawn around the organs of interest in the acquired images and relative radiotracer uptake will be calculated as a percentage (or fraction) of the injected dose per gram of tissue at each timepoint. Blood data will be also collected by measuring (by gamma-counter) the radioactivity of the blood samples withdrawn at the different time points. Tissue activity curves (ACs) will be generated by fitting mono or multi- exponential equations to the organ uptake and blood data.

By integrating such time-activity curve, the Time Integrated Activity Coefficients (TIACs) will be obtained. The TIACs from each organ will be processed by Olinda/EXM software for the calculation of the organ absorbed radiation doses.

## **Safety**

Adverse events and laboratory toxicities occurring during the first cycle of treatment are also considered primary endpoints and the results for GEP-NETs and PPGLs as pooled cohort will be summarized descriptively as defined in [Section 12.5.2](#) to evaluate the acute toxicities induced by a single full-dose Lutathera infusion (7.4 GBq).

### **12.4.2 Statistical model, hypothesis, and method of analysis**

All analyses will be reported descriptively. No statistical hypothesis testing will be performed.

### **12.4.3 Handling of missing values**

Missing data will not be replaced.

The censoring rules will be described in the Statistical Analysis Plan (SAP).

## **12.5 Analysis of secondary endpoints**

### **12.5.1 Comparative assessment of Dosimetry/PK in adolescents and adults**

Pharmacokinetic and the dosimetry data will be collected from the adolescent population and assessed in the context of previously derived adult data. Adolescent pharmacokinetic parameters including (Cmax and AUC0-24) will be compared to those parameters derived from the adult population, to ensure that adolescent values lie within those estimates determined from the adult population. In a similar manner the individual derived dosimetry data from the adolescent patients will be compared to the adult values to ensure that estimates lie within the intervals derived from the adult population. Other methods may also be applied if deemed valuable in the assessment of the adolescent data.

Model based assessments of the individual dosimetry values in light of the individual adolescent creatinine clearance and dose may also be undertaken for comparative purposes.

All adolescent dosimetry and pharmacokinetic data will be pooled and analyzed collectively to ensure covariate effects including age and weight are of limited value in dosimetry prediction. In this way it can be ensured that the pediatric population is adequately characterised by the adult population.

A difference in biodistribution between patients with GEP-NET and PPGL is generally not anticipated, as disease normally does not affect the uptake in organs and normal tissues and thus estimates of absorbed dose. The review of the preliminary dosimetry and safety data already obtained from this study shows a good concordance between adolescent and adult dosimetry patients in line with this hypothesis.

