adolescents. The dose assessment was based primarily on the target organs for radiation toxicities (kidney and bone marrow) ensuring that the selected dose gave kidney dosimetry values below 29 Gy and bone marrow dosimetry values below 2 Gy (see [Section 4.2](#)). Analysis has indicated that the full adult regimen, i.e. 4 doses of Lutathera administered every 8 weeks (7.4 GBq/200 mCi x 4 administrations every 8 weeks; cumulative dose: 29.6 GBq/800 mCi) is appropriate in the adolescent population to keep the median kidney dosimetry within the values outlined above. Importantly, clinical data from the pivotal adult efficacy trials have shown that this full adult cumulative radioactive dose from 4 administrations correlated with efficacy in adult population.

In this adolescent study, dosimetry assessments will be performed in each patient after the first Lutathera dose (or in exceptional circumstances after a later dose in case dosimetry cannot be performed in a particular patient after the first Lutathera dose) to confirm dosimetry values with regard to reference limits ([Section 6.5.1.2](#)) and ensure continuation of safe dosing. In case that the resulting cumulative radiation dose exceeds the reference limits, the DSMB will evaluate benefit risk for the patient and give recommendation on whether dosing can continue and at which level (see [Section 6.5.1](#)). Although the ultimate decision on dose modification remains with the investigator, it is strongly recommended that the investigator follows DSMB recommendations.

The co-primary objectives and endpoints have been selected to meet the main goal of the clinical study to validate the dose extrapolation approach for adolescent patients with GEP-NETs or PPGs. The clinical study will confirm the safety, tolerability and dosimetry findings of the adolescent dose modelled based on the original adult data. Of note, dosimetry is considered as a primary endpoint instead of PK parameters based on the Lutathera mechanism of action.

The secondary objectives and endpoints were selected to evaluate all safety data from cumulative dosing, as well as long-term safety in adolescents (see the rationale for duration of follow-up in [Section 4.3](#)). In addition to safety analysis, a comparative assessment of dosimetry in adolescent patients and adults (from the NETTER-1 study) is selected as a secondary objective in order to evaluate the predicted organ absorbed dose and the accuracy of the model.

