#### 4.2 Rationale for dose/regimen and duration of treatment

The modelling and simulation analysis to define the dose in the adolescent population was based on the clinical data from two adult clinical trials, [REDACTED] and approximately 50 subjects were available for analysis. As the principal Lutathera risks are related to renal and bone marrow toxicities, the key objective in this analysis was to investigate the factors influencing the absorbed dose to the kidneys and bone marrow in adults and extrapolate this to the adolescent population (12 to <18 years old) accounting for adolescent specific factors determined from the adult dosimetry model.

The amount of Lu radioactivity administered to an adult patient has to achieve an optimal therapeutic effect of PRRT in the tumors with limited side effects to radiosensitive organs, namely the kidneys and bone marrow. The true threshold of the kidney-absorbed dose that predisposes patients to toxicity has not been accurately determined. Based on data from external beam radiation, commonly accepted values vary from 18 to 23 Gy (Marks et al 2010, Wessels et al 2008, Emami et al 1991, Emami 2013). However, there is growing evidence that PRRT with lutetium (Lu) oxodotreotide is less nephrotoxic (Konijnenberg et al 2007, Bodei et al 2008, Sundlöv et al 2017, Bergsma et al 2016b, and Löser et al 2018). As an example, results by Sundlöv et al 2017 support the dose limit proposed for high risk patients (concomitant risk factors) of  $27 \pm 2$  Gy, while suggesting that patients without risk factors may support a higher kidney dosimetry value. In a study of 323 patients described by Bergsma et al 2016b, where a median number of four 7.4 GBq cycles of lutetium (Lu) oxodotreotide have been administered, no subacute grade 3 or 4 nephrotoxicity was observed. The mean kidney absorbed radiation dose in this study was  $20.1 \pm 4.9$  Gy. No correlation was observed between radiation-absorbed dose to the kidneys and worsening creatinine clearance on long-term follow-up. A similar outcome was obtained also in the NETTER-1 Phase III study, in which the kidney absorbed radiation dose was  $19.4 \pm 8.7$  Gy, with no clinically relevant kidney toxicity observed and no evidence of correlation between creatinine clearance level and kidney absorbed dose.

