For bone marrow, the commonly accepted threshold is 2 Gy (based on historical cohorts of patients treated with I (Bergsma et al 2016b), and here too the clinical relevance for PRRT with lutetium (Lu) oxodotreotide has not been established. Bergsma et al 2016a described the hematological toxicity findings in 320 patients treated with 4 cycles of lutetium (Lu) oxodotreotide (7.4 Gy each). The bone marrow dosimetry was evaluated in a subset of patients (obtaining a mean bone marrow absorbed dose of  $2.0 \pm 0.2$  Gy) and no correlation was found between cumulative bone marrow-absorbed dose and therapy-related persistent hematologic disorder. Similarly, in the NETTER-1 study, in which the estimated mean bone marrow absorbed dose was  $1.0 \pm 0.8$  Gy, no correlation was found between these two parameters. Moreover, a wide heterogeneity between authors in the methodology of bone marrow dosimetry (planar imaging, SPECT imaging, blood samples) makes it difficult to compare between studies.

In view of the above, it is considered that the total doses of  $\leq 29$  Gy and  $\leq 2$  Gy of lutetium (Lu) oxodotreotide, constitute appropriate thresholds for the kidney and bone marrow-absorbed dose by subject, respectively.

The modelling and simulation analyses were therefore conducted to estimate the projected dose in the adolescent population ensuring that median dosimetry estimates are  $\leq 29$  Gy for the kidney or  $\leq 2$  Gy for the bone for four treatment cycles. Results indicate that the covariates important in explaining kidney dosimetry across the adult population [REDACTED]

[REDACTED] These findings were also supported by the prior analysis of Svensson et al 2015 who indicated that patients with inferior

renal function were exposed to higher renal dosimetry values, and also developed hematological toxicity.

Reference values taken from the literature for creatinine clearance levels in an adolescent population suggested limits from approximately 70 – 108 ml/min ([Piepsz 2008](#)), which are in line with adult values when adjusted by body surface area ([Pottel 2017](#)) indicating similar renal function in these two groups.

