## 12.8 Sample size calculation

No formal sample size or power calculations were made in the context of this safety study. The overall sample size of 8 patients (with a minimum of 3 GEP-NET patients) is deemed sufficient to confirm similar organ dosimetry results in the adolescent population compared to the ones in adults.

Modelling and simulation analysis shows that a mean (standard deviation) of the absorbed dose in the kidney of approximately 18 Gy (SD 8) is expected in the adolescent population ([Section 4.2](#)). Assuming a standard deviation of 8, a sample size of 8 patients will produce a two-sided 95% confidence interval with a distance from the mean to the limits that is equal to 6.688.

Additionally, a sample size of 8 patients produces an adequate probability of observing acute toxicities (See [Table 12-1](#)). Indeed, in the phase III NETTER-1 study grade 3/4 adverse drug reactions related to Lutathera treatment were observed in 30% of patients. The probability to detect similar events assuming a true incidence rate of 30% in this study population is 94.2% with 8 patients.

**Table 12-1 Likelihood of observing at least one patient with acute toxicity for a sample size of 8 patients and incidence of acute toxicities**

| Sample size | Acute toxicities true incidence rate, % |      |      |      |      |
|-------------|---|------|------|------|------|
|             | 10%                                     | 20%  | 30%  | 40%  | 50%  |
| 8           | 57.0                                    | 83.2 | 94.2 | 98.3 | 99.6 |

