## 2.7 Pharmacokinetics and dosimetry analysis supporting secondary objectives

As part of the secondary objectives, PK and dosimetry data will be analysed in the context of the modeling and extrapolation performed using adult data (as detailed in the modeling report). The adult PK (radiolabel plasma concentrations) data was fitted to a two compartment model with a zero-order input and first-order elimination. The adult kidney and bone marrow dosimetry data were described by [REDACTED]

Plots of observed PK and dosimetry data from adolescent participants overlaid with predictions using the adult model will be first generated to evaluate if the pediatric population is adequately characterized by the model from the adult population. Adolescent PK parameters (e.g., CL, Cmax) will also be compared to those parameters derived from the adult population, to ensure that adolescent values lie within those estimates determined from the adult population. Other methods may also be applied if deemed valuable in the assessment of the adolescent data. These analyses will be based on the DAS and PKAS.

Then, pooled analyses using all adolescent and adult participants for dosimetry data will be performed. For that, parameters from the models will be re-estimated based on population-based non-linear mixed effects modeling using appropriate software. Covariates from the adult model (i.e., dose and creatinine clearance for dosimetry modeling) as well as other covariates such as age, weight and body surface area will be re-evaluated and inter-relationships re-assessed. Model qualification will use graphical methods, such as visual inspection of different diagnostic plots, precision of any parameter estimates (estimated  $\pm$  standard error), Visual Predictive Check (VPC) plots (stratified by adult and adolescent populations) as well as decreases in both between-subject variability and residual variability.

Further details on the PK and dosimetry modeling will be given in a separate modeling plan.

Finally, the following model-based PK parameters will be reported for each adolescent participant:

- AUCinf: area under the concentration time curve from 1st administration to infinity
- AUClast: Area under the concentration time curve from 1st administration to the last observed concentration
- Cmax: maximum blood concentration
- tmax: sampling time at which Cmax is reached
- CL: systemic clearance
- V1: Volume of distribution of the central compartment

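### The adult interval used to check adolescent dosimetry is undefined, and no planned analysis is stated to report the size of the adolescent-adult difference with its uncertainty

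*Protocol*

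**What the plan says.** The comparison with adults is a secondary objective. Protocol 4.1 describes it as a "comparative assessment of dosimetry in adolescent patients and adults (from the NETTER-1 study") and gives its purpose as evaluating the predicted organ dose and the accuracy of the model.

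Protocol 12.5.1 sets each adolescent's dosimetry against the adult values "to ensure that estimates lie within the intervals derived from the adult population". It also allows model-based assessments that take account of creatinine clearance and dose, foresees a pooled covariate analysis, and leaves room for other methods.

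SAP 2.7 has the matching sentence, "to ensure that adolescent values lie within those estimates determined from the adult population", but there it concerns PK parameters only. For dosimetry, SAP 2.7 plans overlays on adult-model predictions, re-estimation of the model on pooled adult and adolescent data, and visual predictive checks stratified by population.

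Neither document gives the interval type, its coverage or a required count. Protocol 12.4.2 and SAP 2.5.2 rule out hypothesis testing. Protocol 12.8 nevertheless describes 8 patients as enough to confirm that organ dosimetry is similar to that of adults.

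The 29 Gy kidney and 2 Gy marrow figures belong to a different question. Protocol 4.2 says they "constitute appropriate thresholds for the kidney and bone marrow-absorbed dose by subject, respectively".

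**The concern.** Extrapolation from adults rests on adolescents receiving similar organ doses. Checking whether individual values fall in an adult range does not measure how similar the two groups are. Adult kidney doses vary widely (coefficient of variation 8.7/19.4 = 45%), so a systematic shift of moderate size leaves most adolescents inside the range. If all patients are expected to fall inside, the check also becomes harder to satisfy as patients are added, even when nothing differs.

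Because the interval is undefined, the reading of the result is left open until the data are in. What a reader needs is an estimate of the adolescent-adult difference and how precisely it is known. The plan does not state that it will give one.

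**Working it through.** **Inputs.** Adult kidney dose in NETTER-1: 19.4 Gy, SD 8.7 (Protocol 4.2). Expected adolescent kidney dose: "approximately 18 Gy (SD 8) is expected in the adolescent population" (Protocol 12.8). Adults in the model data: "approximately 50 subjects were available for analysis" (Protocol 4.2). Planned adolescents: 8; enrolled at Amendment 03: 11. Kidney reference limit: 29 Gy (Protocol 6.5.1.2).

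**The plan's own figure.** The half-width of the 95% CI for the mean, with n = 8 and SD 8, is t(0.975; 7 df) × 8/√8 = 6.688 Gy. This reproduces Protocol 12.8.

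**Assumptions for the in-interval check.** (a) The adult interval is mean ± 1.96 SD of individual values. (b) All patients must fall inside. The plan states neither.

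**Interval.** 19.4 ± 1.96 × 8.7 = 2.3 to 36.5 Gy. A lognormal with the same mean and SD gives about 7.7 to 41.0 Gy. Both upper ends exceed 29 Gy.

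**Chance that all patients fall inside.** The formula is pⁿ, where p is the chance for one patient.
- Identical populations: p = 0.95; 0.95⁸ = 66%; 0.95¹¹ = 57%.
- Mean 25% higher (24.25 Gy), SD unchanged: p = Φ((36.45 − 24.25)/8.7) − Φ((2.35 − 24.25)/8.7) = 0.914; 0.914⁸ = 49%; 0.914¹¹ = 37%.
- Mean 50% higher (29.1 Gy), SD unchanged: p = 0.800; 0.800⁸ = 17%.

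**Sensitivity for all 8 inside.**

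| Model | Identical | +25% | +50% |
|---|---|---|---|
| Normal, same SD | 66% | 49% | 17% |
| Lognormal | 66% | 51% | 25% |
| Normal, SD scaled with the mean | 66% | 27% | 5% |

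**A different reading of the interval.** If it meant the 95% CI of the adult mean (16.9 to 21.9 Gy, taking 50 adults), all 8 would fall inside with probability below 0.001 even when the populations are identical. The result depends heavily on a definition the documents do not give.

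**Precision of a ratio of geometric means.** From the adolescent planning values, log-SD = √ln(1 + (8/18)²) = 0.42. With 8 adolescents and about 50 adults, the standard error of the log ratio is 0.4246 × √(1/8 + 1/50) = 0.162. The 95% CI factor is exp(2.00 × 0.162) = 1.38, so the CI runs from about 0.72 to 1.38 times the estimate. Using 19.4 and 8.7 instead gives log-SD 0.43 and a factor of 1.39. With 11 adolescents the CI is about 0.75 to 1.33 times the estimate.

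**The case against.** The strongest reply is that Protocol 12.5.1 contains no pass rule. It does not require every patient to fall inside and does not say that similarity will be declared, and the study is descriptive throughout. This stands: the probabilities above describe one plausible reading, not a written criterion.

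It is also true that the in-interval check is not the only comparison. The overlays, the pooled model with creatinine clearance, age, weight and body surface area, and the stratified predictive checks could all show a shift. SAP 2.7 refers to a modelling report and a separate modelling plan, and some predicted values are redacted, so an interval may be defined elsewhere. But in the documents at hand none of these analyses has a criterion or is stated to yield an adolescent-adult difference with its uncertainty.

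Two stronger readings are tempting. A reader might infer that a shifted dose would pass almost as often as an equal one. The figures do not support that: 66% against 49% is a real drop, and at +50% the chance is 17-25% or lower. A reader might also infer that the plan accepts kidney doses above 29 Gy. It does not. A patient whose cumulative dose exceeds the limit goes to DSMB review (Protocol 6.5.1.2), and the interim analysis looks for a median below 29 Gy (Protocol 12.7).

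The ratio has limits too. With 8 patients, a true 25% increase would exclude a ratio of 1 only about one time in four. A raw ratio is also affected by eligibility: this trial excludes creatinine clearance below 70 mL/min and NETTER-1 below 50 (Protocol 4.4). Hence the adjusted version in the fix.

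**Conclusion.** The point holds as a gap in definition and reporting. The interval is undefined, and no planned analysis is stated to quantify the adolescent-adult difference with its uncertainty.

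Under the two stated assumptions, the in-interval check discriminates poorly for moderate shifts. Identical populations fail it about one time in three, while a 25% higher mean with unchanged SD passes it about half the time. It separates better at +50%, or if the SD rises with the mean.

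The 36 Gy upper end matters only for interpretation: being inside the adult interval must not be reported as being within the 29 Gy limit. Nothing here bears on dosing or on the DSMB process.

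**What to change.** In Protocol 12.5.1 and SAP 2.7:

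- Define the adult interval as a prediction interval with stated coverage, for example 95%. Report the number of adolescents outside it as supportive information.
- Make the main descriptive comparison the adolescent-to-adult ratio of geometric means with a 95% CI, for kidney dose, marrow dose, AUC and CL. Give it unadjusted and, from the pooled model, adjusted for creatinine clearance and dose.
- Keep the overlays and visual predictive checks. State that the 29 Gy and 2 Gy limits are assessed separately.

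No hypothesis test is needed, and the adult data already underlie the model. The cost is a wording change and one extra table. The drawback is a wide interval, about 0.72 to 1.38 times the estimate with 8 adolescents and about 50 adults, which shows how much 8 patients can say.
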